### **Main Outcome Measures**

The primary outcome measure was the mean change in corneal surface staining (guided by use of fluorescein and lissamine green) at weeks 1, 2, 4, 8 and 12 based on the NEI grading scale. Corneal fluorescein staining was graded from 0 to 3 (none to heavy) in five regions of the cornea and summed for a total score.

All secondary outcome measures followed the same timeline with comparison at weeks 1, 2, 4, 8 and 12 in comparison to baseline. Secondary outcome measures included the mean change in tear break-up time (TBUT), the mean change in conjunctival staining (graded 0-3 in 6 regions), the mean change in tear osmolarity as measured by TearLab, the mean change in DEQ-5, the mean change in meibomian gland scores as measured by quality of meibum expression, the mean change in best-corrected distance visual acuity (BCDVA) as measured by ETDRS chart and the mean change in Schirmer's score as measured by a Schirmer's test strip.

Meibomian gland scoring involved grading the quality of expression (0-3) from 15 glands along the lower eyelid including temporal, central and nasal. For scoring, 3 was representative of clear, liquid secretions and 0 was no secretions. The DEQ-5 Dry Eye Questionnaire was used to evaluate symptoms and characterize severity of discomfort, dryness and tearing. Possible scores ranged from 0 to 22 with higher scores representing worse symptoms.

On the screening visit and the initiation of therapy including implantation of the dexamethasone insert in the study group, a physician ease of insertion questionnaire was also completed by the physician implanting the device. All device-related complications were recorded. All subject-reported adverse events were recorded at each study visit.

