### **Statistical Analysis**

All statistical analysis was performed using Prism 9 software (GraphPad Software, Inc.). Repeated measures analysis of variance was performed to compare the values at each time point in each group. Post hoc analyses were also performed with Bonferroni correction to directly compare the mean values at each time point in comparison to baseline. A *P* value less than 0.05 was considered statistically significant.

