## **RESULTS**

### **Patient Demographics**

Sixty eyes of 30 subjects were successfully enrolled into the study including 20 eyes of 10 subjects in the dexamethasone/cyclosporine group, 22 eyes of 11 subjects in the loteprednol/cyclosporine group and 18 eyes of 9 subjects in the cyclosporine monotherapy group. All 3 groups were summarized by baseline characteristics, which are shown in Table 2.

None of the three groups, including the study and two control groups met the primary endpoint. In the dextenza group, the mean baseline corneal staining score was  $0.5 \pm 1.0$  with 70% ( $n=14$ ) without evidence of corneal staining at baseline. The mean score at weeks 4, 8 and 12 was  $0.6 \pm 1.0$  ( $P = 0.99$ ),  $0.5 \pm 1.1$  ( $P = 0.99$ ) and  $0.7 \pm 1.4$  ( $P = 0.97$ ), respectively. In the loteprednol group, the mean baseline corneal staining score was  $0.8 \pm 1.5$  with 64% ( $n=14$ ) without corneal staining at baseline. At weeks 4, 8 and 12, the mean score was  $0.9 \pm 0.9$  ( $P = 0.99$ ),  $0.0 \pm 0.0$  ( $P = 0.06$ ) and  $0.6 \pm 1.0$  ( $P = 0.78$ ), respectively. In the cyclosporine monotherapy group, the mean baseline corneal staining score was  $0.5 \pm 0.5$  with 50% ( $n=9$ ) of eyes absent of any corneal staining at baseline. There was no significant change in corneal staining at any time point with a mean score of  $1.1 \pm 1.4$  ( $P = 0.26$ ),  $0.3 \pm 0.6$  ( $P = 0.63$ ) and  $0.5 \pm 0.7$  ( $P = 0.99$ ) at weeks 4, 8 and 12, respectively. These results, in addition to comparisons of other outcome measures, are summarized in Table 3.

There was no significant change in conjunctival staining, Schirmer scores, TBUT, tear osmolarity or meibomian gland scores at any of the follow-up time points in comparison to baseline in all three groups. These results are summarized and also demonstrated in Table 3.

Across all visits, the mean IOP remained stable in all three groups. In the cyclosporine monotherapy group, there were no instances of IOP elevation  $>10$  mmHg above baseline. Similarly, in the dextenza and loteprednol groups, there were no instances of IOP elevation  $>10$

mmHg above baseline at any time point. There were no canalicular-related complications or adverse events related to implantation of the dexamethasone insert. No patients required removal of the insert.

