To evaluate symptoms, a subjective questionnaire, DEQ-5, was administered at each time point. At baseline, the mean DEQ score was  $14.1 \pm 4.0$ ,  $14.4 \pm 2.4$  and  $14.4 \pm 3.7$  in the dextenza, loteprednol and cyclosporine monotherapy groups, respectively. In the dextenza group, the mean DEQ score improved to  $10.6 \pm 4.6$  ( $P = 0.22$ ),  $11.3 \pm 4.5$  ( $P = 0.19$ ) and  $10.3 \pm 6.3$  ( $P = 0.20$ ) and weeks 4, 8 and 12, respectively but the change was not statistically significant. In the loteprednol group, there was a significant improvement in the DEQ score with a mean score of  $11.0 \pm 2.4$  ( $P < 0.01$ ),  $9.1 \pm 4.0$  ( $P < 0.01$ ), and  $10.2 \pm 3.8$  ( $P < 0.01$ ), at weeks 4, 8 and 12, respectively. Similarly, there was an improvement in the DEQ score in the cyclosporine monotherapy from baseline at weeks 8 ( $10.6 \pm 2.6$ ,  $P < 0.01$ ) and 12 ( $9.4 \pm 3.1$ ,  $P < 0.01$ ), but the change at 4 weeks ( $12.2 \pm 2.2$ ,  $P = 0.39$ ) was not statistically significant.

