## DISCUSSION

This prospective, randomized, open-label clinical study evaluated the use of an intracanalicular 0.4 mg dexamethasone insert in combination with topical cyclosporine 0.05% for the treatment of dry eye. Although the efficacy of this combination remains unclear based on the results of this pilot study, the results of this study support the safety of this approach without any adverse events, no IOP spikes above baseline and no device-related complications.

Topical cyclosporine 0.05% has been shown to provide an improvement in tear production and dry eye-related symptoms but many patients in clinical trials leading to its approval reported a delay in symptomatic relief. As a delay in relief can contribute to reduced compliance, providers may initiate adjuvant use of topical steroids in combination with topical cyclosporine 0.05% and studies evaluating this combined regimen reported findings of quicker symptomatic relief and more rapid improvement of objective parameters such as Schirmer testing and corneal staining. No groups in this study met the primary endpoint, however, patients in the loteprednol group reported a significant improvement in symptoms as measured by the DEQ-5 questionnaire, consistent with prior studies evaluating the combined use of corticosteroids and topical cyclosporine 0.05%. The dextenza group also noted an improvement in symptoms, but the change was not statistically significant. An improvement in symptoms with a combination of cyclosporine 0.05% and corticosteroids corroborates what has previously been reported.

Several prior studies have highlighted the safety and efficacy of the dexamethasone insert evaluated in this present study with regards to postoperative pain and inflammation following cataract surgery. However, multiple recent studies have described use of the insert beyond the postoperative setting including a recent report describing the combined use of thermal pulsation therapy with the dexamethasone insert for the treatment of meibomian gland dysfunction. To our knowledge, this is the first study evaluating the adjuvant use of the dexamethasone insert in combination with cyclosporine 0.05%. Although this present study did not yield any significant results, we anticipate future studies will involve the dexamethasone insert evaluating its utility in the treatment of dry eye.

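### Secondary endpoints are tested at 0.05 with no correction over endpoints or arms and no link to the unmet primary, so DEQ-5 should be reported as nominal and exploratory, not as a confirmed significant improvement

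*SAP*

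**What the plan says.** The SAP, written in the past tense and already containing results, names one primary outcome (corneal staining) and seven secondaries under Main Outcome Measures: tear break-up time, conjunctival staining, tear osmolarity, DEQ-5, meibomian gland score, best-corrected distance acuity (BCDVA) and Schirmer score. On timing it says "All secondary outcome measures followed the same timeline with comparison at weeks 1, 2, 4, 8 and 12".

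Statistical Analysis gives three rules that bear on error control:

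- The model is run arm by arm: "Repeated measures analysis of variance was performed to compare the values at each time point in each group".
- Visits are corrected: "Post hoc analyses were also performed with Bonferroni correction to directly compare the mean values at each time point in comparison to baseline".
- The threshold is general: "A *P* value less than 0.05 was considered statistically significant".

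No order of testing, gate on the primary, or correction over endpoints or arms is stated. The protocol has no statistical section that could supply one.

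In the Results, "None of the three groups, including the study and two control groups met the primary endpoint". Five other secondaries are then reported as unchanged in all arms, and no BCDVA result appears. For DEQ-5 in the loteprednol arm, "there was a significant improvement in the DEQ score with a mean score of" 11.0, 9.1 and 10.2 at weeks 4, 8 and 12 from a baseline of 14.4, each with P < 0.01. Monotherapy has P < 0.01 at weeks 8 and 12 and P = 0.39 at week 4. The dexamethasone insert arm is reported as not significant. The Discussion repeats that "patients in the loteprednol group reported a significant improvement in symptoms as measured by the DEQ-5 questionnaire". Later in the same section it says the study gave no significant results.

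**The concern.** Bonferroni over visits holds each endpoint in each arm at about 5%. With seven endpoints and three arms there are 21 such chances, and the rule treats each as sufficient for the word significant. Once the primary has failed, nothing in the plan says what status a secondary P value has. The Results and Discussion fill that gap by giving DEQ-5 the same unqualified label a primary result would carry, and the Discussion adds that it agrees with earlier studies.

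What is at stake is how far the symptom finding can be relied on. DEQ-5 is the only outcome the report calls significantly improved. A reader who takes the label at face value will assume an error rate of 5% for the set of secondary claims, and the plan does not deliver that.

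**Working it through.** The plan states no familywise error rate, power or sample-size calculation, so there is no figure of its own to reproduce beyond the per-test 0.05 (taken as two-sided).

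**1. Inputs.** From the SAP: 7 secondaries, 3 arms, 5 planned visits (3 displayed), and 10, 11 and 9 patients (20, 22 and 18 eyes). Arms contain different patients, so they are independent. Assumed, because the documents give no values: the correlation between endpoints within an arm, and between visits.

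**2. Families.** 7 × 3 = 21 endpoint-by-arm families, each held at about 0.05 by the visit correction.

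**3. Independent families, all nulls true.** 1 − 0.95^21 = 65.9%. For the six secondaries with printed results (18 families), 1 − 0.95^18 = 60.3%. For one arm alone (7 families), 1 − 0.95^7 = 30.2%.

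**4. Correlated endpoints.** With equicorrelated normal statistics within an arm and independent arms, the 21-family figure is:

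| Endpoint correlation | 0 | 0.3 | 0.5 | 0.6 | 0.8 | 0.9 |
|---|---|---|---|---|---|---|
| At least one false positive | 66% | 61% | 54% | 50% | 38% | 30% |

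It crosses 50% at a correlation of about 0.59, or about 0.51 if only the six reported secondaries are counted.

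**5. Simulation with the visit correction.** I used patient-level t tests on change from baseline, 10/11/9 patients, 3 or 5 visits and 20,000 runs per setting. At visit correlation 0.3 to 0.5, the rate is 53% to 65% for endpoint correlation 0 to 0.6, and 42% to 45% at 0.8. When visits are very alike (correlation 0.8), Bonferroni over visits is conservative and the rates fall to 41% to 56% and 32% to 35%.

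**6. The pattern actually reported.** In the same null runs, some endpoint reaching visit-adjusted P < 0.01 at all three displayed visits in some arm occurs in 0.03% of runs or fewer at visit correlation up to 0.5, and in at most about 0.5% at 0.8. Three or more of five visits occurs in at most about 1.1%.

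**7. Corrected thresholds.** On the visit-adjusted P: 0.05/7 = 0.0071 for seven endpoints within one arm, and 0.05/21 = 0.0024 for all families. A printed P < 0.01 settles neither.

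**8. DEQ-5, loteprednol arm, from the summary data.** I took SD of change = √(s0² + s1² − 2·r·s0·s1), t = mean change/(SD/√n), and P × 3 for the displayed visits. The baseline-to-visit correlation r is assumed, 0 to 0.7.

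- Weakest case, week 12, r = 0, n = 11: SD = √(2.4² + 3.8²) = 4.49; t = 4.2/(4.49/√11) = 3.10; P = 0.0113; × 3 = 0.034.
- Strongest case, week 8, r = 0.7, n = 11: SD = √(5.76 + 16 − 13.44) = 2.88; t = 5.3/(2.88/√11) = 6.1; P = 0.00012; × 3 = 0.00035.
- Week 8, n = 11, at r = 0, 0.3 and 0.5: × 3 gives 0.011, 0.0040 and 0.0015.
- n = 22 eyes: × 3 is at most 0.0008 at any visit.

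Patient-level values fall on both sides of 0.0071 and 0.0024. Eye-level values pass both, but only by counting each patient's questionnaire score twice. Multiplying by 5 for the planned visits moves the patient-level range to 0.0006 to 0.056.

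**The case against.** The strongest reply is that the 50% to 66% belongs to a different event. It is the chance of any single false positive among 21 families when nothing changes. The report shows P < 0.01 at three visits in one arm and two in another, on the same endpoint. A reader might infer that the DEQ-5 finding is more likely than not to be false; the documents do not support that, and step 6 points the other way for patient-level tests. This part of the reply stands.

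Three other tempting inferences also fail:

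- *That DEQ-5 was picked out by its P value.* Selection is not shown. Five other secondaries are openly reported as not significant, DEQ-5 is the only symptom measure among the SAP's secondaries, and protocol section 1.2 hypothesises symptomatic improvement.
- *That DEQ-5 was the only secondary below 0.05.* This cannot be known, because no BCDVA result is printed.
- *That DEQ-5 fails correction.* P < 0.01 gives only upper bounds: 0.07 after multiplying by seven and 0.21 after multiplying by 21. These show that exact values are missing, not that the result fails.

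It is also fair that the Discussion calls this a pilot, describes efficacy as unclear and attaches the label to a control arm, not the insert arm. A gate behind the primary is a confirmatory-trial convention. That limits the harm, but the Statistical Analysis section never calls the secondary P values exploratory. Nor is the count of seven inflated: protocol section 2.2 lists eight secondaries, including MMP-9 and conjunctival injection, which the SAP drops.

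**Conclusion.** The point holds as a matter of the status given to secondary results. The stated rule leaves the set of secondaries with a false-positive chance of about 50% to 66% if all nulls are true and within-arm endpoint correlation is 0 to 0.6, and about 30% to 45% at 0.8 to 0.9. Those correlations are assumptions, and very high correlation between visits would lower the figures somewhat further. Even 30% is six times the nominal 5%.

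This does not make the DEQ-5 result false. It may survive correction over seven endpoints or over all 21 families, but the report does not let a reader tell, because it prints only P < 0.01 and does not say whether n was patients or eyes. With the primary unmet and no rule for the secondaries, the unqualified claim of significant improvement is not supported as a confirmed finding. The Discussion's two statements on significance cannot both stand.

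**What to change.** 1. In the SAP's Statistical Analysis section, add a sentence, marked as a clarification made after the results were known: *secondary P values are nominal and exploratory; they are adjusted over visits but not over endpoints or arms.* The marking matters, because an undated change to the rule now would itself be post hoc.
2. State in the same place whether the unit of analysis was the patient or the eye, and how many visits the Bonferroni factor covers.
3. In the DEQ-5 paragraph of the Results and in the Discussion, replace the significance wording with the within-arm mean change, its 95% CI and the exact nominal P at each visit.
4. Reconcile the Discussion's claim of a significant DEQ-5 improvement with its later statement that the study gave no significant results.

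The cost is wording, plus exact P values and intervals from data already held. The downside is that DEQ-5 loses the unqualified label significant. The result itself stays in the report, in a form a reader can check against 0.0071 or 0.0024.

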## **RESULTS**

### **Patient Demographics**

Sixty eyes of 30 subjects were successfully enrolled into the study including 20 eyes of 10 subjects in the dexamethasone/cyclosporine group, 22 eyes of 11 subjects in the loteprednol/cyclosporine group and 18 eyes of 9 subjects in the cyclosporine monotherapy group. All 3 groups were summarized by baseline characteristics, which are shown in Table 2.

None of the three groups, including the study and two control groups met the primary endpoint. In the dextenza group, the mean baseline corneal staining score was  $0.5 \pm 1.0$  with 70% ( $n=14$ ) without evidence of corneal staining at baseline. The mean score at weeks 4, 8 and 12 was  $0.6 \pm 1.0$  ( $P = 0.99$ ),  $0.5 \pm 1.1$  ( $P = 0.99$ ) and  $0.7 \pm 1.4$  ( $P = 0.97$ ), respectively. In the loteprednol group, the mean baseline corneal staining score was  $0.8 \pm 1.5$  with 64% ( $n=14$ ) without corneal staining at baseline. At weeks 4, 8 and 12, the mean score was  $0.9 \pm 0.9$  ( $P = 0.99$ ),  $0.0 \pm 0.0$  ( $P = 0.06$ ) and  $0.6 \pm 1.0$  ( $P = 0.78$ ), respectively. In the cyclosporine monotherapy group, the mean baseline corneal staining score was  $0.5 \pm 0.5$  with 50% ( $n=9$ ) of eyes absent of any corneal staining at baseline. There was no significant change in corneal staining at any time point with a mean score of  $1.1 \pm 1.4$  ( $P = 0.26$ ),  $0.3 \pm 0.6$  ( $P = 0.63$ ) and  $0.5 \pm 0.7$  ( $P = 0.99$ ) at weeks 4, 8 and 12, respectively. These results, in addition to comparisons of other outcome measures, are summarized in Table 3.

There was no significant change in conjunctival staining, Schirmer scores, TBUT, tear osmolarity or meibomian gland scores at any of the follow-up time points in comparison to baseline in all three groups. These results are summarized and also demonstrated in Table 3.

Across all visits, the mean IOP remained stable in all three groups. In the cyclosporine monotherapy group, there were no instances of IOP elevation  $>10$  mmHg above baseline. Similarly, in the dextenza and loteprednol groups, there were no instances of IOP elevation  $>10$

mmHg above baseline at any time point. There were no canalicular-related complications or adverse events related to implantation of the dexamethasone insert. No patients required removal of the insert.

To evaluate symptoms, a subjective questionnaire, DEQ-5, was administered at each time point. At baseline, the mean DEQ score was  $14.1 \pm 4.0$ ,  $14.4 \pm 2.4$  and  $14.4 \pm 3.7$  in the dextenza, loteprednol and cyclosporine monotherapy groups, respectively. In the dextenza group, the mean DEQ score improved to  $10.6 \pm 4.6$  ( $P = 0.22$ ),  $11.3 \pm 4.5$  ( $P = 0.19$ ) and  $10.3 \pm 6.3$  ( $P = 0.20$ ) and weeks 4, 8 and 12, respectively but the change was not statistically significant. In the loteprednol group, there was a significant improvement in the DEQ score with a mean score of  $11.0 \pm 2.4$  ( $P < 0.01$ ),  $9.1 \pm 4.0$  ( $P < 0.01$ ), and  $10.2 \pm 3.8$  ( $P < 0.01$ ), at weeks 4, 8 and 12, respectively. Similarly, there was an improvement in the DEQ score in the cyclosporine monotherapy from baseline at weeks 8 ( $10.6 \pm 2.6$ ,  $P < 0.01$ ) and 12 ( $9.4 \pm 3.1$ ,  $P < 0.01$ ), but the change at 4 weeks ( $12.2 \pm 2.2$ ,  $P = 0.39$ ) was not statistically significant.

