3. STUDY DESIGN

3.1. Study Description and Duration

This prospective, open-label, single-center, non-randomized, investigator-sponsored clinical study seeks to investigate the benefit of managing patients with DED with a sustained release intracanalicular dexamethasone (0.4 mg) insert in addition to Restasis compared to Restasis in conjunction with Lotemax and Restasis alone. In addition, this study will evaluate the ease of DEXTENZA® insertion.

After screening a given patient for inclusion and exclusion criteria, and gaining informed consent, both eyes will be prescribed Restasis. Both eyes of 10 patients will be selected to receive DEXTENZA® insertion (study group), while 10 patients will be prescribed Lotemax and 10 patients will be on Restasis monotherapy (control groups). Per patient, the study period will last for approximately 12 weeks after the DEXTENZA® insertion, consisting of one screening/prescription visit and 5 post-procedure follow-up visits (week 1, week 2, week 4, week 8 and week 12). At week 1, week 2, week 4, week 8 and week 12, primary and secondary endpoints will be assessed alongside standard-of-care procedures. Adjusting for enrollment period, the study will last a total of approximately 9 months.

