## Patients

60 eyes of 30 patients age  $\geq 18$  with clinically diagnosed aqueous-deficient dry eye disease and determined to be a candidate (based on clinical judgment) for treatment with a topical immunomodulator were enrolled in the study.

Patients were excluded if they had been on topical immunomodulation therapy in the 3 months prior to screening, were actively being treated with topical, oral or intravenous immunosuppressive agents, had a hypersensitivity to dexamethasone, had active infectious systemic or ocular disease or had altered nasolacrimal flow of either acquired or congenital origin. Pregnant patients were also excluded.

Following screening and informed consent, patients were randomized into 3 groups; a study group and 2 control groups. Each group included 10 patients. The study group was started on cyclosporine 0.05% and was implanted with an intracanalicular, 0.4 mg dexamethasone insert in both eyes. The first control group was started on cyclosporine 0.05% in conjunction with topical loteprednol 0.5% twice daily. The 2nd control group was started on cyclosporine 0.05% as monotherapy.

The study period lasted 12 weeks including one screening/prescription visit and follow-up visits which occurred at weeks 1, 2, 4, 8 and 12 following initiation of therapy. At weeks 1, 2, 4, 8 and 12 the primary and secondary endpoints were assessed.

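### The unit of analysis is not stated, and the primary endpoint, corneal staining, was evidently tested with a patient's two eyes as independent units

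*SAP*

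**What the plan says.** The SAP's Statistical Analysis section is the only account of the analysis; the protocol has no statistical section. It states: "Repeated measures analysis of variance was performed to compare the values at each time point in each group". It adds: "Post hoc analyses were also performed with Bonferroni correction", for each time point against baseline. It does not define the repeated subject. It mentions no averaging of eyes, choice of a study eye, or model for paired eyes.

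Treatment is assigned to the patient. SAP, Patients, says the study group was "implanted with an intracanalicular, 0.4 mg dexamethasone insert in both eyes", and Protocol 3.1 also has both eyes of each patient treated. (The screening list in Protocol 5.1.1 mentions insertion in one eye; these passages must be reconciled.) SAP, Patient Demographics, gives the group sizes as "20 eyes of 10 subjects in the dexamethasone/cyclosporine group, 22 eyes of 11 subjects in the loteprednol/cyclosporine group", with 18 eyes of 9 subjects on monotherapy.

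Under Main Outcome Measures, corneal fluorescein staining is "graded from 0 to 3 (none to heavy) in five regions of the cornea and summed for a total score", so each eye's score is a whole number.

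**The concern.** Two eyes of one patient, given the same treatment, usually respond alike. If they enter a test as independent units, the sample size is overstated and, under positive between-eye correlation, standard errors and P values are too small. This bears on the primary endpoint, where the smallest printed P value (loteprednol, week 8, 0.06) lies just above the 0.05 threshold. A reader also cannot tell which n lies behind the statement that the other eye-level outcomes did not change.

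**Working it through.** **1. Summary by eye.** SAP, Patient Demographics, counts eyes or subjects without baseline staining as 14 (70%), 14 (64%) and 9 (50%). 14/20 = 70.0%, 14/22 = 63.6% and 9/18 = 50.0%. The counts of 14 exceed the 10 and 11 patients, and the monotherapy figure is explicitly "of eyes absent of any corneal staining at baseline".

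**2. Reproducing the printed P = 0.06.** Loteprednol corneal staining is 0.8 ± 1.5 at baseline and 0.0 ± 0.0 at week 8 (SAP Results text and Table 2). With complete data each change is minus the baseline score, so the SD of change is 1.5. Paired test: t = 0.8/(1.5/√n), df = n − 1, two-sided, times 3 for the three reported follow-up visits.

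- 22 eyes: t = 2.50, P = 0.0207, ×3 = **0.062** (0.036 to 0.102 over rounding of mean and SD).
- 11 patients, SD 1.5: t = 1.77, P = 0.107, ×3 = **0.32** (0.24 to 0.42 over rounding).

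**3. Could the eyes have been averaged first?** Averaging can shrink the SD, so the possible data were enumerated. With 14 zeros among 22 whole-number scores, 8 eyes are non-zero. A mean of 0.8 needs a sum of 17 or 18, and the SD must lie in 1.45 to 1.55. Nine score patterns qualify. At eye level they give 0.049 to 0.077 with three comparisons and 0.081 to 0.129 with five, so three fits 0.06 and five does not. The nine patterns can be paired into 11 patients in 381 distinct ways. A test on patient means (df 10, ×3) gives:

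- 0.083 to 0.359 in all 292 pairings with non-negative between-eye (intraclass) correlation;
- 0.06 in only 12 pairings, all with negative correlation (−0.23 to −0.10).

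**4. Other explanations.**

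- *Pooled ANOVA error.* With a common standard error, the ratio of t values equals the ratio of mean changes. P = 0.06 at week 8 and 0.78 at week 12 need a ratio of 0.46 to 0.49 (three comparisons) or 0.54 to 0.57 (five), for 11 or 22 units. The printed means allow (0.75 − 0.65)/0.75 = 0.13 to (0.85 − 0.55)/0.85 = 0.35. It fits neither n.
- *Uncorrected P values.* Dextenza at week 12 has P = 0.97, with 0.7 ± 1.4 against a baseline of 0.5 (text) or 0.6 (Table 2), SD 1.0. The smallest non-zero mean change with whole-number scores is 1/20 = 0.05. An uncorrected P of 0.97 with 10 patients (t = 0.0387, df 9) then needs a change SD of 0.05 × √10/0.0387 = 4.1, and more with 20 eyes. The largest possible is about 1.0 + 1.4 = 2.4.

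**5. Other printed P values.** The implied SD of change is S = |d|√n/t, with t taken at P/3. The implied baseline/visit correlation is r = (s₁² + s₂² − S²)/(2s₁s₂).

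| Result | Printed P | r if eyes | r if patients |
|---|---|---|---|
| Staining, monotherapy, week 4 | 0.26 | 0.18 (n = 18) | 0.97 (n = 9) |
| Staining, monotherapy, week 8 | 0.63 | 0.31 (n = 18) | 0.69 (n = 9) |
| DEQ-5, Dextenza, week 4 | 0.22 | −0.84 (n = 20) | 0.20 (n = 10) |
| DEQ-5, monotherapy, week 4 | 0.39 | −0.98 (n = 18) | 0.20 (n = 9) |

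The staining values are more plausible by eye, and the DEQ-5 values by patient. The unit therefore seems to change between endpoints without being stated. Conjunctival staining, Schirmer, TBUT, osmolarity and meibomian scores have no printed P values. One of them fits eyes poorly: monotherapy meibomian scores (9.2 ± 2.6 to 7.2 ± 1.4 at week 4, not significant) need r of −0.21 or less with 18 eyes, but only 0.65 or less with 9 patients.

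**6. Size.** The between-eye correlation ρ is not given, so it is assumed over 0 to 1. The SD of a two-eye mean is 1.5√((1 + ρ)/2), with n = 11, df 10, ×3. The factor by which the eye-level SE is too small is √(1 + ρ), and the effective number of eyes is 22/(1 + ρ).

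| ρ | SE factor | Effective eyes | Week-8 P |
|---|---|---|---|
| 0 | 1.00 | 22 | 0.09 |
| 0.25 | 1.12 | 17.6 | 0.15 |
| 0.5 | 1.22 | 14.7 | 0.21 |
| 0.9 | 1.38 | 11.6 | 0.30 |
| 1 | 1.41 | 11 | 0.32 |

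At ρ = 0 the move from 0.06 to 0.09 reflects only the loss of degrees of freedom (21 to 10). The table uses the rounded mean and SD; the whole-number pairings in step 3 reach 0.359.

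**The case against.** The main objection is that nothing turns on this. The SAP says that no group met the primary endpoint and lists the small sample as a limitation; under positive correlation, a correction only makes a null result more null. That stands, and it limits the weight of the point.

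The inference can also be attacked. It leans on one unusual cell: all zeros at week 8, between 0.9 at week 4 and 0.6 at week 12. No n per visit is printed, and missing eyes at week 8 would break the step that equates change with baseline. The multiplier of three is inferred from the fit, although five follow-up visits were planned. P = 0.99 is printed four times, which suggests truncated values or another adjustment. These are real assumptions, but they do not change the direction: a Sidak correction for three comparisons gives 0.061 by eye, and the monotherapy staining P values point to eyes without using the week-8 loteprednol cell.

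Finally, uncorrected tests on patient means would give 0.06 in 58 of the 381 pairings, all with positive between-eye correlation (0.23 to 0.55). But this contradicts the SAP's stated Bonferroni correction and cannot produce the Dextenza week-12 value of 0.97. Counts of eyes alone would show only how the data were described; it is the reproduced P value that indicates the unit of the test.

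**Conclusion.** The concern holds. That the unit is unstated is plain from the text. That corneal staining was tested by eye is an inference, held with high confidence for that endpoint only. It rests on complete data, three comparisons and a separate variance per comparison. With positive between-eye correlation the printed staining P values are too small. The loteprednol week-8 value of 0.06 would be about 0.09 to 0.32 at patient level over an assumed correlation of 0 to 1; the other staining P values cannot be recomputed from the printed figures. DEQ-5 appears to have been analysed by patient, and the unit for the remaining eye-level outcomes can be neither shown nor excluded. No reported conclusion reverses.

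**What to change.** In the Statistical Analysis section, name the patient as the unit of analysis for every endpoint. Rerun all eye-level outcomes on the mean of the two eyes per patient per visit (n = 10, 11 and 9), or with a mixed model that has a patient random effect and eye nested in patient. Print the n and the number of Bonferroni comparisons beside each set of P values.

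The cost is one or two sentences and a rerun on existing data. P values and intervals will become less favourable under positive between-eye correlation. A mixed model on 9 to 11 patients with many zero scores may be unstable, so the patient mean is the simpler choice.
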